2.2 Study product Profile

2.2.1 Investigational product description

Sculptra Aesthetic is a poly-L-lactic acid implant in the form of a suspension, which is reconstituted from a sterile dry powder by the addition of sterile water for injection. Poly-L-lactic acid (PLLA) is the main active ingredient from which the product has achieved its intended purpose. Sodium carboxymethylcellulose (CMC) acts as a suspending agent for maintaining an even distribution of PLLA particles following reconstitution. Mannitol enhances the lyophilization process and provides the suspension with a consistency that is suitable for injection.

Each vial of dry powder contains 150 mg PLLA, 90 mg CMC and 127.5 mg non-pyrogenic mannitol – in total a vial weight of 367.5 mg and is per approved label to be reconstituted prior to use by the addition of 5 mL of SWFI to form a sterile non-pyrogenic suspension. (2) In this study, commercially available *Sculptra Aesthetic* labeled for the study will be used and reconstitution will be made with 8 mL of SWFI with addition of 1 mL of 2% lidocaine prior to injection. It has been recommended by experienced physicians to evaluate alternative reconstitution procedures for *Sculptra Aesthetic* compared to the

currently approved instructions for use, primarily to enhance safety of the device by potentially reducing incidence of nodule and papule formation. [\(3\)](#)

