2.4 Risks and benefits

Anticipated benefits for subjects treated with *Sculptra Aesthetic* for the correction of cheek wrinkles include restoration of a more youthful appearance, relatively long-lasting effects that would reduce the need for frequent touch-up procedures. Another benefit is better knowledge about the safety profile for *Sculptra Aesthetic* in the new reconstitution volume, including assessment of the risks for late onset papules, nodules, and granuloma as well as other potential adverse event cases associated with *Sculptra Aesthetic*.

The benefit of *Sculptra Aesthetic* for correction of cheek wrinkles is also being evaluated in the ongoing, post-approval US clinical study (US10321). [\(4\)](#) Although treatment in the cheek area was secondary to treatment in the nasolabial folds in this study, the interim data results support that treatment for cheek wrinkles is effective and well tolerated.

Since the initial approval of *Sculptra Aesthetic* in 1999 (EU), the amount of SWFI used to reconstitute *Sculptra Aesthetic* has gradually increased. Based on medical literature and physician experience, practitioners have reported improved clinical outcomes with increased reconstitution volumes that are up to two times higher than the volume recommended by the manufacturer and usually in combination with anesthetic solutions, like lidocaine 2%. [\(3, 5\)](#) It has also been suggested, that a reduction in frequency of nodules/papules can be achieved with an increased reconstitution volume. [\(6, 7\)](#).

Most recently, the increased reconstitution volume for treatment of nasolabial folds was evaluated in study 43USSA1705.

Risks with *Sculptra Aesthetic* as with any other injectable implant include infections, perforation of blood vessels, trauma to nerves and lumps. The most common reported adverse events (AEs) after *Sculptra Aesthetic* treatments are formation of papules and nodules, swelling, mass/induration, of which most resolve with time.

Infection, and damage to body structures such as nerves or blood vessels at the injection site, have also been reported. Rare but serious AEs associated with the intravascular injection of soft tissue fillers in the face have been reported and include temporary or permanent vision impairment, blindness, cerebral

ischemia or cerebral hemorrhage, leading to stroke, skin necrosis, and damage to underlying facial structures.

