10.5 Safety analysis

Number and percentage of subjects reporting each pre-defined, expected, post-treatment symptoms, as collected in the 28-day diary, will be presented in total and by maximum intensity. Number of days with the event will be presented by treatment group and category: 1, 2-7, 8-14, and 15-28 days.

All AEs will be coded according to MedDRA and summarized by system organ class (SOC), preferred term (PT) and treatment.

AEs related to study product or injection procedure and unrelated AEs will be presented by maximum intensity, SOC and PT. For related AEs, the number of days to onset and the duration of event will be summarized by SOC and PT using mean, SD, min, max and median. Action taken for related AEs will also be summarized by SOC and PT. Serious AEs will be listed.

In addition, a summary of all AEs will be provided, which will include (but is not limited to):

- number of subjects with at least one AE and number of events (in total as well as serious AEs)

- number of subjects with at least one related AE and number of events (in total as well as serious AEs)
- number of subjects with at least one un-related AE and number of events (in total as well as serious AEs)
- number of subjects who did not have an AE

Functionality, sensation, firmness, symmetry, mass formation and palpation assessments will be analyzed descriptively as appropriate.

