2.1.1 Programming Conventions

CCI [REDACTED] will have responsibility for performing analyses. All computations for statistical analyses will be performed using SAS® software, Version 9.4 or later. All SAS programs used in the production of statistical summary outputs will be validated with independent programming prior to finalization. In addition, all program outputs will be independently reviewed. The validation process will be used to confirm that all data manipulations and calculations were accurately done. Once validation is complete, a senior statistical reviewer will perform a final review of the documents to ensure the accuracy and consistency with this plan and consistency

Effective date: 2022-03-08 18:10

Effective

Version: 2.0

within tables. Upon completion of validation and quality review procedures, all documentation will be collected and filed by the project statistician or designee.

The electronic case report form (eCRF) data for all subjects will be provided in Standard Data Tabulation Model (SDTM) datasets. Analysis Data Model (ADaM) datasets will be developed from the SDTM datasets for use in table and figure production.

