2.5.3 Adverse Events (AEs)

All AEs will be coded according to MedDRA and summarized by system organ class (SOC) and preferred term (PT) for each treatment group.

Typically, only AEs that occur during the extension period will be summarized. A summary of all related AEs that includes those occurring from the pivotal study to end of the extension study will be provided for Group B only.

AEs related to study product or injection procedure and unrelated AEs will be presented by maximum intensity, SOC and PT. For related AEs, the number of days to onset and the duration of event will be summarized by SOC and PT using mean, SD, min, max and median. Action taken for related AEs will also be summarized by SOC and PT. Serious AEs will be listed.

In addition, a summary of all AEs will be provided, which will include (but is not limited to):

- number of subjects with at least one AE and number of events (in total as well as serious AEs)
- number of subjects with at least one related AE and number of events (in total as well as serious AEs)
- number of subjects with at least one un-related AE and number of events (in total as well as serious AEs)
- number of subjects who did not have an AE

Adverse events will also be summarized by the following subgroups:

- Study Center
- Age Group (<55 years vs. \geq 55 years)
- FST Skin Type
- Injection Technique (including techniques of Bolus, Fanning, Cross Hatching, Linear Antegrade, etc. and all observed combinations of these [e.g. Bolus * Fanning, Bolus * Linear Retrograde, Cross Hatching * Fanning * Linear Retrograde, etc.]).
- Pre-Treatment CCI

Adverse events of special interest (all incidences of visual disturbances, regardless of relationship to study product or seriousness) will be summarized. Adverse events related to study product or injection procedure will be summarized by session.

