2.5.4 Other Safety Analyses

Visual function will be summarized by visit, along with each visit's change from pre-treatment (Group A only), and 95% confidence intervals, via t-distribution, will be provided for the change.

Functionality, sensation, firmness, symmetry, mass formation, palpation assessments, and device deficiencies will be analyzed descriptively as appropriate.

The incidence of nodules, papules, and granuloma (defined as AEs with system organ class containing "nodule", "papule", or "granuloma") will be summarized, including the time to onset from the pre-treatment visit as well as the duration.

[figure not shown]
Weight and BMI will additionally be summarized at each visit along with change from the pre-treatment visit.

Effective date: 2022-03-08 18:10

Effective

Version: 2.0

2022-03-08 18:10

Effective date:

Effective

Version: 2.0

[figure not shown]
Statistical Analysis Plt

CCI

GALDERMA
EST. 1981

4 Rasch Transformation of FACE-Q

CCI

Statistical Analysis Fl

CCI
GALDERMA
EST.1981

5 Schedule of Events (Treatment and Control Groups)

Table 1. Schedule of events, **Group A** (subjects receiving Treatment in 43USSA1812ext)

	Visit 5 ¹ Final Study Visit 43USSA1812	Visit 1 ² Extension Study Entry Treatment 1	Visit 1a: Telephone Contact	Visit 2: Month 13 Treatment 2 ⁴ (Optional)	Visit 2a: Telephone Contact ⁷	Visit 3: Month 14 Treatment 3 ⁸ (Optional)	Visit 3a: Telephone Contact ⁷	Visit 4: Month 15 Treatment 4 ⁹ (Optional)	Visit 4a: Telephone Contact ⁷	Visit 5: Month 19 Follow-up	Visit 6: Month 21 Follow-up	Visit 7: Month 24 Final visit/ Early termination
	Month 12 (± 2 weeks) after Baseline	(± 2 weeks) after Visit 5	72 hours (± 24 hrs) after Treatment 1	1 month (± 2 weeks) after Treatment 1	72 hours (± 24 hrs) after Treatment 2	1 month (± 2 weeks) after Treatment 2	72 hours (± 24 hrs) after Treatment 3	1 month (± 2 weeks) after Treatment 3	72 hours (± 24 hrs) after Treatment 4	7 months (± 2 weeks) after ext. Visit 1	9 months (± 2 weeks) after ext. Visit 1	12 months (± 2 weeks) after ext. Visit 1
Informed consent		X										
Inclusion/Exclusion criteria		X ⁴		X ⁴		X ⁴		X ⁴				
Demographics incl. weight	X	X ³								X ³	X ³	X ³
Concomitant therapies	X	X	X	X	X	X	X	X	X	X	X	X
Urine pregnancy test ^{4,5}	X			X		X		X				
Photography (2D and 3D)	X	X ⁴		X ⁴		X ⁴		X ⁴		X	X	X
Sculptra Aesthetic administration		X		X ⁶		X ⁶		X ⁶				
Adverse event assessment	X	X	X	X	X	X	X	X	X	X	X	X
Safety Assessments ¹¹	X	X		X		X		X		X	X	X

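### SAP 2.5.4 selects nodules, papules and granuloma by MedDRA system organ class instead of preferred term, so the rule as written cannot pick out these events

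*SAP*

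**What the plan says.** SAP section 2.5.4 (Other Safety Analyses) defines the events to be summarized: "The incidence of nodules, papules, and granuloma (defined as AEs with system organ class containing" one of three words, namely nodule, papule or granuloma. The summary reports incidence, "including the time to onset from the pre-treatment visit as well as the duration".

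Elsewhere the plan uses SOC and PT as two distinct levels. SAP section 2.5.3 states: "All AEs will be coded according to MedDRA and summarized by system organ class (SOC) and preferred term (PT) for each treatment group". Protocol section 10.5 does the same: "All AEs will be coded according to MedDRA and summarized by system organ class (SOC), preferred term (PT) and treatment". On timing, SAP section 2.5.3 restricts itself to related events: "For related AEs, the number of days to onset and the duration of event will be summarized by SOC and PT".

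Neither document, in its visible text, defines nodules, papules or granuloma by PT, by reported term or by a list of terms. Under SAP section 2.1 the SAP prevails over the protocol's statistical sections, so the wording of 2.5.4 governs.

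**The concern.** The selection rule is applied at the wrong level of the dictionary. Taken literally, it yields an empty table or, for any SOC whose name did match, a table of everything under that SOC. An empty table would also contradict the PT tables in the same report if any nodule, papule or granuloma is recorded.

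These events are not incidental here. Protocol section 2.2.1 explains that alternative reconstitution procedures were recommended for evaluation "primarily to enhance safety of the device by potentially reducing incidence of nodule and papule formation". Protocol section 2.4 counts better knowledge of safety at the new volume as a benefit, "including assessment of the risks for late onset papules, nodules, and granuloma", and lists papules and nodules among the most commonly reported adverse events. SAP 2.5.4 is the only visible place that plans a summary dedicated to them.

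**Working it through.** The plan gives no figure to reproduce, so the check applies the rule literally and then counts what depends on it.

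**1. What the rule can do, with no assumption about SOC names.** Let *n*ₖ be the number of adverse events under SOC *k*. Let *g*ₖ = 1 if the name of SOC *k* contains one of the three words, and 0 otherwise. The number selected is Σ *g*ₖ*n*ₖ. Because *g*ₖ depends only on the SOC name, each SOC contributes 0 or *n*ₖ, that is, 0% or 100% of its events. The rule therefore cannot separate a nodule from another event under the same heading.

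**2. What it selects, given SOC names.** The documents specify MedDRA but do not print its SOC names. Assuming the standard list of 27, a text search for the three words finds 0 matches. Then every *g*ₖ = 0, and the number selected is 0 whatever the data. How many events a PT-based search would select cannot be computed from the documents.

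**3. Planned onset and duration summaries covering these events.** Inputs: SAP 2.5.3 gives onset and duration by SOC and PT for related events only. SAP 2.5.4 is not limited by relatedness.

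| Events | SAP 2.5.3 | SAP 2.5.4 | Planned | Left if 2.5.4 is empty |
|---|---|---|---|---|
| Related | 1 | 1 | 1 + 1 = 2 | 1 + 0 = 1 |
| Unrelated | 0 | 1 | 0 + 1 = 1 | 0 + 0 = 0 |

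Incidence by SOC and PT in SAP 2.5.3 is unaffected.

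**4. Whether the PT tables can stand in.** They show each PT separately. A subject with both a nodule and a papule appears in two PT rows (1 + 1 = 2) but is 1 subject, so the rows cannot be added to give the number of subjects with any of these events. SAP 2.5.4 does not say whether it intends such a combined figure. If it does, that figure is lost as well.

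**5. Time origin.** SAP 2.5.4 measures onset from the pre-treatment visit, which for Group B is Day 1 of the pivotal study (SAP 2.4.2). SAP 2.5.3 refers to days to onset without naming an origin. The dedicated summary is therefore the one whose stated clock bears most directly on late onset.

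**The case against.** The best defence is that this is a one-phrase slip with an obvious intent. The sentence names the events and gives the search words, and a programmer would probably notice an empty table. SAP 2.1.1 requires independent programming and independent review of outputs, and adds that "a senior statistical reviewer will perform a final review of the documents to ensure the accuracy and consistency with this plan"; the sentence goes on to cover consistency within tables. An empty table beside PT rows that show nodules would reveal itself and could not silently bias a result.

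The stakes are also limited. The summary is descriptive, and it appears neither among the listed safety endpoints (SAP 1.6, protocol 3.2) nor in protocol 10.5. No group in this extension receives the labelled dilution, so the table could not test a reduction in nodules.

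Much of the information survives elsewhere:

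- The events remain in the SOC and PT tables, the summary of related events by session, and the listings.
- For Group B there is a summary of related events from the pivotal study onward.
- Mass formation is recorded as an adverse event (protocol 8.5.3), and Group A's diary lumps and bumps are displayed separately (protocol 8.2).

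Table formats are in a companion document that was not available, and part of the SAP is redacted, so a term list could exist there.

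Most of this stands, and it limits the size of the problem. It does not make the rule correct. Review against the plan is weak protection when the plan itself is wrong. If a programmer quietly switches to PT, which terms count is settled outside the SAP, possibly with the data in view. The documents describe related findings in several ways (mass or induration, lumps and bumps, aggregated material), so that choice is not trivial.

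**Conclusion.** The concern holds. The rule in SAP 2.5.4 is wrong as written: on any set of SOC names it takes all or none of the events under a heading. On the assumption that no standard SOC name contains the three words, it selects 0.

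The consequence is moderate. The individual events are not lost, and incidence by PT is intact. The loss is the dedicated incidence summary and, for events judged unrelated, the only planned summary of onset and duration. The documents do not indicate how many such unrelated events to expect. The conclusion is confined to the visible text. This should be fixed, because the events concerned are ones the protocol singles out and the correction is nearly free.

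**What to change.** In SAP 2.5.4, replace system organ class with preferred term. That alone cures the error. Two small additions make the summary reproducible:

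- Fix the list of qualifying PTs before database lock, after a brief medical review, since a bare word search could miss events coded under terms such as mass or induration.
- State whether the three event types are shown combined (each subject counted once), separately, or both.

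Under SAP 2.1 this is one short SAP amendment if made before lock, and otherwise a documented change in the clinical study report. The visible text does not give the lock date. No new data are needed and no other table changes.

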8.5.3 Mass formation

Mass formation in the cheeks will be assessed by a study staff member that is qualified by training and experience to perform safety assessments at Enrollment and at all physical visits. Mass formation will be defined as lumps or aggregation of coherent material. An assessment of mass formation is to be recorded as an adverse event.

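### The SAP's nodule, papule and granuloma summary searches system organ class instead of preferred term, and even at preferred-term level it would omit AEs coded only as mass, lump or induration

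*SAP*

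**What the plan says.** SAP 2.5.4 (Other Safety Analyses) plans a summary of "The incidence of nodules, papules, and granuloma", covering incidence, time to onset and duration. The events are "defined as AEs with system organ class containing 'nodule', 'papule', or 'granuloma". Mass, lump and induration are not search words.

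The preceding paragraph of that section covers the staff assessments: "Functionality, sensation, firmness, symmetry, mass formation, palpation assessments, and device deficiencies will be analyzed descriptively as appropriate".

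SAP 2.5.3 tabulates all AEs by system organ class and preferred term. For related AEs it adds onset and duration at those levels.

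Protocol 8.5.3 has qualified staff check for mass formation at enrollment and at every physical visit: "Mass formation will be defined as lumps or aggregation of coherent material. An assessment of mass formation is to be recorded as an adverse event".

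Protocol 2.4 describes the most commonly reported AEs as "formation of papules and nodules, swelling, mass/induration, of which most resolve with time". The same section gives the safety knowledge expected from the study as "including assessment of the risks for late onset papules, nodules, and granuloma".

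**The concern.** The dedicated summary is the only planned place where these lesions are pooled across terms. It bears on a stated reason for studying the more dilute suspension: Protocol 2.2.1 says the alternative reconstitution is of interest mainly because it might reduce nodules and papules, and Protocol 2.3 says the extension is meant to characterise that suspension over the long term.

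Two features of the search rule work against this purpose. It is applied at a dictionary level where lesion words would not be expected. And its word list omits the name under which the protocol has staff look for lumps. Either feature can only lower the count. A reader who took the resulting incidence as the rate of lumps in the cheek could be misled.

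**Working it through.** The documents give no rate or count for any of these events, so there is no stated figure to reproduce. The check is a comparison of definitions.

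**Step 1: the level searched.** SAP 2.5.4 matches on system organ class. SAP 2.5.3 names system organ class and preferred term as two levels of the same coding. The documents do not list the class names. I assume that they name body systems and not lesions, as the term implies. An AE coded to a preferred term containing *nodule* would then sit under a class whose name does not contain that word, and the rule would not select it. Read literally, the summary would be empty or nearly so. Adding words to the list at this level would not help.

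**Step 2: the word list, once the level is corrected.** Suppose the search runs on preferred term.

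| Term to which the AE is coded | Contains nodule, papule or granuloma? | In the summary? |
|---|---|---|
| Nodule, papule or granuloma term | Yes | Yes |
| Mass term only | No | No |
| Lump term only | No | No |
| Induration term only | No | No |

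Protocol 8.5.3 creates AEs from lumps found by staff, and Protocol 2.4 expects mass/induration events to be common. The last three rows are therefore not hypothetical categories.

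**Step 3: can the pooled count be recovered elsewhere?**

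- *AE tables (SAP 2.5.3).* Each preferred term has its own row. A subject with a nodule and a mass is counted in both, so adding rows does not give the number of subjects with any lump. Onset and duration are given for related AEs only.
- *Mass-formation assessments (SAP 2.5.4).* These are summarised, but no onset or duration is specified.
- *Diary.* Lumps/bumps are asked about directly for 28 days after each treatment. Protocol 8.2 keeps diary data apart from AE data, and SAP 1.3.6 says only Group A receives diaries.

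None of these gives a de-duplicated count of subjects with any lump, and no planned table reconciles them.

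**Step 4: size.** This cannot be estimated from the documents. As an illustration only, suppose the level has been corrected, a share *s* of subjects with any lump have AEs coded solely to mass, lump or induration terms, and the true any-lump incidence is 10%. Then:

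reported incidence = true incidence × (1 − *s*)

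- *s* = 25%: 10% × 0.75 = 7.5%
- *s* = 50%: 10% × 0.50 = 5%
- *s* = 75%: 10% × 0.25 = 2.5%

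Both the 10% and the shares are assumptions. Under the rule as now written the figure would be close to zero whatever *s* is.

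**The case against.** The strongest reply is that the three words match the protocol's question. Protocol 2.4 names late-onset papules, nodules and granuloma as the interest, and Protocol 2.2.1 speaks of nodules and papules. Protocol 2.4 also lists mass/induration as a separate item, so it need not be the same lesion. Adding it changes the quantity reported. This stands, and it is why the three-term count should be kept and the wider count shown beside it.

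Second, a reader might infer that lumps drop out of the safety report, or that a principal safety measure is affected. The documents support neither. Mass formation is itself a listed safety endpoint (Protocol 3.2, SAP 1.6), it is summarised in SAP 2.5.4, and as an AE it enters the SAP 2.5.3 tables. The nodule summary sits under Other Safety Analyses and is not a listed endpoint. What is missing is a pooled count.

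Third, a reader might infer that the protocol directs sites to a word the search misses. Protocol 8.5.3 says "An assessment of mass formation is to be recorded as an adverse event" but does not prescribe the AE term. An investigator may enter the finding as a nodule, which a term-level search would catch. Coding is left to the data management plan (Protocol 9.1), and the AE recording instructions in Protocol 8.6.4 are incomplete in the public text. An undercount is therefore possible, not shown.

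Fourth, a reader might infer that onset and duration are understated too. Leaving out events shifts their averages in no known direction, so that does not follow.

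Finally, no decision rule depends on this. Safety analysis is descriptive (SAP 2.5), and the extension has no standard-dilution arm against which to test a reduction. This limits the consequence but does not make the search rule work.

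**Conclusion.** The point holds in two parts.

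1. The rule in SAP 2.5.4 searches the wrong dictionary level and, read literally, would capture few or no of the events it is meant to count. This rests on the assumption that system organ class names do not contain lesion words, which fits the SAP's own separation of the two levels.
2. At preferred-term level, AEs coded only as mass, lump or induration would still fall outside the summary, although the protocol defines mass formation as lumps, requires it to be recorded as an AE and expects mass/induration to be common. As a measure of lumps, the pooled incidence may be understated. The amount depends on site wording and coding and cannot be estimated from the documents.

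The affected events remain visible elsewhere in the report. The change should be made because it is cheap and because the rule fails as written, not because safety data would otherwise be lost.

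**What to change.** In SAP 2.5.4:

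- Replace system organ class with preferred term (or reported term) as the level searched.
- Keep the three-term nodule, papule and granuloma count as planned.
- Add separate rows for AEs in the treated area whose term contains *mass*, *lump* or *induration*.
- Add one combined row, counting each subject once for any of the six terms, with time to onset and duration.
- Cross-check the combined count against subjects with a positive mass-formation assessment at any visit, and list the disagreements.

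The cost is a rewritten definition sentence, a wider text search and a few table rows, with no new data collection. Under SAP 2.1 the change is an SAP amendment if made before database lock, and otherwise is documented in the clinical study report. The downside for the sponsor is that the combined figure will be higher than the three-term figure. Showing both side by side lets readers see why.
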